This protocol is written to describe the procedures for a single 5, 6 or 7 year follow-up control visit of patients that participated in the 12-month SCHEDULE-study and the following 3-year follow-up examination/visit. The aim of this 5 to 7-year follow-up visit is to examine the effect of long term treatment, i.e. 5, 6 or 7 years, with early initiation of everolimus (Certican®) and early elimination of cyclosporine (CsA), compared to standard immunosuppressive regimen including CsA, on renal and heart function. During the time period of this follow-up examinations this visit will be performed as part of a routine annual visit 5, 6 or 7 years since transplantation (and inclusion in the original SCHEDULE study).

PROTOCOL FOR THE 5 TO 7-YEAR FOLLOW-UP EXAMINATION

1 INTRODUCTION

1.1 Background

The calcineurin inhibitors (CNIs) have contributed to low acute rejection rates and favourable short-term graft survival in heart transplantation (HTx) with 80-90% patients survival after 12 months. However, the protective role of these and other immunosuppressive drugs in the development of cardiac allograft vasculopathy is uncertain; in fact CNIs and steroids have been implicated in the pathological development of this condition. In addition, new long term adverse effects have occurred including CNI-induced nephrotoxicity. Nearly 30% of HTx recipients demonstrate renal dysfunction already at 1 year post-HTx. Importantly, a glomerular filtration rate (GFR) <60 mL/min/1.73 m² at this time point has been shown by our own group to be an independent risk factor for both all-cause and cardiac mortality (1).

Everolimus, a proliferation signal inhibitor (PSI) is a potent, rapamycin-related immunosuppressive agent that exerts its immunosuppressive effect by blocking interleukin (IL-2 and IL-5) driven proliferation of T and B cells. PSIs do not share the nephrotoxic properties of CNIs, but potential serious side effects such as exacerbation of proteinuria, impaired wound healing and pulmonary inflammation have been reported.

As attention shifts towards improving long-term outcomes in thoracic transplant recipients, there is a growing emphasis on maintenance immunosuppressive regimens that minimize exposure to CNIs (2). CNI-related renal toxicity (3) is of particular concern in view of the high rate of chronic renal failure observed in heart and lung transplant recipients (4), but other CNI-related complications such as diabetes mellitus, hyperlipidemia, hypertension and infections can also adversely affect outcomes. Importantly, progressive renal disease, metabolic abnormalities and infections contribute to the risk of cardiac allograft vasculopathy (CAV) (5), the leading cause of death after the first year following HTx (6). Rapid progression of CAV in the first 5 years as well as in the first year after transplantation detected by intravascular ultrasound (IVUS) analysis is a powerful predictor for mortality, myocardial infarction, and the development of angiographic abnormalities (7, 8).

The introduction of PSIs has created a novel opportunity to limit CNI exposure without loss of efficacy.

Follow-up Examinations

Extension phase of important studies are not uncommon, including in transplantation studies. Data of this kind have been published from other large outcome HTx studies (9, 10, 11). This form of studies allows a more complete evaluation of the effect of treatment as well as side effects.

The results from the SCHEDULE 3-year follow-up visit indicated that the beneficial effect of everolimus treatment with early CNI withdrawal on renal function in *de novo* heart transplant recipients seen at 12 months after transplantation (12) was maintained at 3 years after transplantation (13). The aim of this 5 to 7-year follow-up visit is therefore to further examine the long term effect (i.e. 5 to 7-years) of the combination of everolimus followed by early Cyclosporine A (CsA) withdrawal compared to standard immunosuppressive regimen including CsA, on renal function and progression of CAV.

1.2 Study Purpose

To evaluate, in *de novo* heart transplant recipients, whether early initiation of everolimus and early elimination of CsA compared to standard immunosuppressive regimen including CsA can improve long-term renal function and slow down the progression of CAV.

2 AIMS/OBJECTIVES

The major aim of this extension study is to evaluate the long-term (i.e. 5 to 7 years) effect of early initiation of everolimus and early elimination of CsA compared to standard immunosuppressive regimen including CsA on primary and secondary endpoints investigated in the SCHEDULE main study. The endpoints for this 5 to 7-year follow-up visit are:

Primary endpoint:

- Renal function as assessed by measured glomerular filtration rate (mGFR)

Secondary endpoints:

- Progression of CAV by IVUS analysis
- Myocardial structure and function by echocardiography assessment
- Quality of life by SF-36 (Minnesota Living with Heart Failure Questionnaire), Euro Quality of Life 5D (EQ 5D), and Beck Depression Inventory (BDI) form
- Number of adverse events (AEs)/serious adverse events (SAEs)

3 STUDY DESIGN

The 12-months SCHEDULE main study was a prospective, multi-center, randomized, controlled, parallel group, open label study in *de novo* heart transplant recipients. The study consisted of two study periods, period 1 (HTx to week 7-11) and period 2 (week 7-11 to Month 12). Patients fulfilling the inclusion and exclusion criteria were randomized to one of two treatment groups: (i) conventional treatment with CsA, mycophenolate mofetil (MMF), and corticosteroids (Group A), or (ii) low-dose CsA, everolimus, MMF, and corticosteroids (Group B). After period 1, CsA was discontinued in Group B (experimental set-up with off-label use of everolimus), while the standard triple-drug immunosuppressive regimen was maintained in Group A.

In the 12-month SCHEDULE-study, 115 patients were randomized and treated. The main study was followed by a 3-year follow-up visit in which 102 of the 115 patients participated.

This 5 to 7-year follow-up visit is a further longtime follow-up examination of the patients participating in the SCHEDULE main study and the 3-year follow-up visit.

4 MATERIAL AND METHODS

4.1 Patients

Inclusion criteria:

- Patients who participated in the SCHEDULE 12-month main study, and who completed the 3 year follow-up visit,
- Patients who are coming for a regular annual clinic visit 5 to 7 years after randomization in the main study
- Obtaining of a separate signed patient informed consent will be required for participation in this follow-up examination.

Exclusion criterium:

- Patients with a retransplanted heart since the original SCHEDULE study

The patients will be allocated the same patient number as in the main study. The patients were recruited from six transplant centers in Norway, Sweden and Denmark. Since this is a single visit control there are no withdrawal criteria.

4.2 Treatments

After randomization in the main study patients in Group A received an immunosuppressive regimen consisting of CsA, MMF and corticosteroids in both study periods. Patients in Group B commenced on an immunosuppressive regimen consisting of low dose everolimus and CsA, MMF and corticosteroids in period 1. In period 2 the patients were subjected to abrupt and complete CNI withdrawal, to a CNI free immunosuppressive regimen consisting of everolimus, MMF and corticosteroids.

After completion of the main study (12-months), most of the patients continued on the same immunosuppression. However, patients might have switched to alternative immunosuppressive drugs between Month 12 in the main study, the 3-year follow-up visit, and the 5 to 7-year follow-up visit.

4.3 Efficacy assessments

The assessments to be performed at the 5 to 7-year follow-up visit are presented in Table 1. The same clinical methods/investigations as used for the 12-month assessments (Visit 11) and the 3-year follow-up will be used at the 5 to 7-year follow-up visit. Data from the main study and from the 3 year follow-up visit will also be used.

• Table 1 Assessment Schedule

Visit	Follow-up
Time after randomization	5 to 7 years
Informed consent	X
Baseline data	X
Concomitant therapy	X
Immunosuppressive therapy	X
12-led ECG	X
Vital signs	X
Echocardiography	X
Quality of life	X
IVUS ^{1,2}	X
Laboratory test hematology/biochemistry ³	X
Laboratory test/lipid profile ⁴	X
Urinalysis ⁵	X
██████████	██████████
mGFR	X
Drug concentration trough levels:	
CsA	X
Tacrolimus	X
Everolimus	X
Drug daily doses:	
CsA	X
Tacrolimus	X
Everolimus	X
Corticosteroids	X
MMF	X
AEs	X
SAEs	X

ECG, electrocardiogram; IVUS, intravascular ultrasound; ██████████; mGFR, measured glomerular filtration rate; CsA, cyclosporine; MMF, mycophenolate mofetil; AEs, adverse events; SAEs, serious adverse events

1. Measurements of microcirculation to be performed in connection with routine coronary angiography prior to IVUS examination (optional)
2. If IVUS is not performed as part of the assessments made at the follow-up study visit 5 or 6 years after transplantation IVUS may be collected at the subsequent regular annual routine visit
3. Hematology: hemoglobin, leukocytes, thrombocytes. Biochemistry: ASAT, ALAT, Urea, Creatinine, Uric acid, Sodium, Potassium, Albumin
4. Laboratory tests/Lipid profile: Total cholesterol, LDL-cholesterol, HDL-cholesterol, triglycerides, HbA1c, NT-proBNP, Troponin T, CRP
5. Urinalysis: Albumin/creatinine ratio

4.3.1 Baseline Data for the Follow-up Visit

The following demographic/baseline data will be collected at the follow-up visit:

- Patient number (randomization number in the main study)
- Date of visit
- Patient informed consent (date of obtained ICF) or the reason for not giving consent (i.e. death, patient unwilling to give consent, other reason)

[figure not shown]
4.3.2 Immunosuppressive Medication and Other Concomitant Medications

Present (at the time of the 5 to 7-year follow-up visit) immunosuppressive treatment (everolimus, CsA/tacrolimus, MMF, and corticosteroids [i.e. prednisolone]) including daily dose, information on start and/or stop of immunosuppressive treatment since the end of the original study and reasons for stopping/starting the immunosuppressive drugs will be collected. Present concomitant medications including indication and route of administration will also be collected.

4.3.3 Renal Function

Measured Glomerular Filtration Rate

Renal function will be assessed by mGFR using the same method as used in the main study (chrome-Ethylenediaminetetraacetic acid [Cr-EDTA] clearance, technetium ^{99m}Tc-Diethylenetriaminepentaacetic acid [^{99m}Tc-DTPA] clearance, or lohexol clearance).

Urine Spot Sample

A spot sample (dipstick) will be used for determination of proteinuria (albumin/creatinine ratio).

4.3.4 Intravascular Ultrasound and Cardiac Function

Intravascular Ultrasound Measurements

Intravascular ultrasound (IVUS) will only be performed on patients who have done IVUS examinations in the main study and at the 3-year follow-up visit.

Note: If IVUS is not performed as part of the assessments made at the follow-up study visit 5 or 6 years after transplantation IVUS may be collected at the subsequent regular annual routine visit.

IVUS recordings will be performed in connection with a routine left sided heart catheterization using special catheters. Semi-automated contour detection of both the lumen and external elastic membrane (EEM) will be performed at intervals of 60 frames using dedicated software (QIVUS Clinical Edition, Medis Medical Imaging, Leiden, Netherlands). The longest possible segment between the most distal and proximal side branch visualized in the IVUS pullback will be analyzed for each patient. Following automatic contour detection, borders will be edited manually by two independent operators according to the guidelines for acquisition and analysis of IVUS images by the American College of Cardiology and European Society of Cardiology.

The following parameters will be recorded for all patients using the mean result of all frames analyzed:

- lumen cross-sectional area (CSA)
- vessel CSA
- intimal CSA
- maximal intimal thickness (MIT)

The CSA measurements will be utilized to calculate total atheroma volume using Simpson's method, as well as percent atheroma volume (PAV). The PAV value will be used for defining CAV.

Echocardiography

Standard echocardiography assessment as done in the main study will be performed.

Patients will be examined in the lateral recumbent position after 15 minutes of rest. The heart will be visualized by standard ultrasonic techniques and acoustic windows giving a total homodynamic and valvular assessment.

Three heartbeats will be needed for this analysis. Analysis will be done blinded. Standard measurements including left ventricular end systolic dimension (LVESD) and left ventricular end diastolic dimension (LVEDD), , left ventricular performance assessed as fractional shortening (FF%), and left ventricular ejection fraction (LVEF) (Simpson's method) will be performed. Local echocardiographic recordings will be recorded, echocardiographic recordings may also be read centrally.

4.3.5 Vital Signs

Body weight (kg), height (cm), systolic and diastolic blood pressure (mmHg; seated after at least 20 minutes of rest), and heart rate (beats/min) will be recorded.

4.3.6 Electrocardiogram

A standard 12-lead electrocardiogram (ECG) will be performed, and the following ECG parameters will be documented: type of rhythm, heart rate, PQ time, and QRS interval.

4.3.7 Cardiac rejections

Number and grading of biopsy proven and treated rejections and rejections with hemodynamic compromise since the 3 year follow-up visit will be collected.

4.3.8 Laboratory Evaluations

Hematology, Biochemistry and Urinalysis

The following laboratory parameters will be analyzed:

Hematology: hemoglobin, leukocytes, platelets.

Biochemistry: serum creatinine, urea, uric acid, sodium, potassium, alanine aminotransferase (ALAT), aspartate aminotransferase (ASAT), albumin.

Lipid profile/laboratory tests: total cholesterol, LDL-cholesterol, HDL-cholesterol, triglycerides, HbA1c, NT-proBNP, Troponin T, C-reactive protein (CRP).

Urinalysis: albumin/creatinine ratio, see Section 4.3.3.

Drug Concentration Trough Levels

Whole blood levels (C-0 levels) will be measured for everolimus, CsA, and tacrolimus as part of the routine laboratory measurements.

4.3.9 Health-related Quality of Life

Quality of life will be examined using three validated questionnaires, i.e. the SF-36, EQ 5D, and the BDI form.

4.4 Statistics

The primary efficacy analysis will be based on the intention-to-treat (ITT) population. Statistical hypothesis testing will be performed, and confidence interval (CI) will be derived to estimate the effects. Two-sided tests will be performed on the 5% level of significance, and 95% two-sided CI for least square mean will be presented.

The null hypothesis is that there is no difference in the mean of mGFR between the everolimus arm ($\mu_{\text{Everolimus}}$) and the control arm (Control) (μ_{Control}) and the alternative hypothesis is that there is a difference between everolimus and control at the 5 to 7-years follow-up visit.

$$H_0: \mu_{\text{Everolimus}} - \mu_{\text{Control}} = 0$$

$$H_1: \mu_{\text{Everolimus}} - \mu_{\text{Control}} \neq 0$$

The above between-group comparisons will be performed using an ANCOVA with study treatment (Everolimus, Control) and randomization strata (mGFR above/below 60 mL/min and have/not have mechanical assist device) as classification variables. In addition, the mGFR values at baseline (Visit 6) will be used as covariate.

In general data will be summarised by means of summary statistics. For continuous data, the following summary statistics will be presented: number of observations, mean value, standard deviation, minimum, first quartile, median, third quartile and maximum value. Categorical data will be presented as counts and percentages. Summary statistics will be presented by treatment group/total and assessment visit, as applicable. Individual patient data will be listed.

The analyses of the data from the 5 to 7-year follow-up visit will be presented in a statistical analysis plan (SAP) prepared prior to database lock.

Data sets to be analysed:

The Safety Set will consist of patients who:

- were included in the Safety Set in the Clinical Study Reports Addendum dated 11 August 2015 for the 3 year follow-up visit
- have at least one assessment at the 5 to 7-year follow-up visit

The Intention-to-Treat (ITT) set will consist of patients who:

- were included in the ITT in the Clinical Study Reports Addendum dated 11 August 2015 for the 3 year follow-up visit
- have at least assessment of the efficacy variable mGFR [REDACTED] at the 5 to 7-year follow-up visit

The Per Protocol Set (PPS) will consist of patients who:

- were included in the PPS in the Clinical Study Reports Addendum dated 11 August 2015 for the 3 year follow-up visit
- have at least assessment of the efficacy variable mGFR [REDACTED] at the 5 to 7-year follow-up visit
- are on their randomized treatment i.e. Everolimus or Control (Control=Cyclosporine and/or Tacrolimus) at the 5 to 7-year follow-up visit
- have no major protocol deviation at the 5 to 7-year follow-up visit. The final criteria for PPS, regarding which protocol deviations that warrant exclusions, will be determined when all data on protocol deviations are available and will be documented in a separate document before database lock

The Extended PPS will consist of patients who:

- were included in the ITT in the Clinical Study Reports Addendum dated 11 August 2015 for the 3 year follow-up visit
- have at least assessment of the efficacy variable mGFR [REDACTED] at the 5 to 7-year follow-up visit
- are on their randomized treatment i.e. Everolimus (Everolimus=Everolimus or Everolimus and Cyclosporine and/or Tacrolimus) or Control (Control=Cyclosporine and/or Tacrolimus [and not Everolimus]) at the 5 to 7-year follow-up visit
- have no major protocol deviation at the 5 to 7-year follow-up visit. The final criteria for PPS, regarding which protocol deviations that warrant exclusions, will be determined when all data on protocol deviations are available and will be documented in a separate document before database lock

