3 EFFICACY AND SAFETY ENDPOINTS

3.1 Primary Efficacy Endpoint

The primary endpoint is renal function as assessed by measured glomerular filtration rate (mGFR) 5-7 years after randomization.

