4 OVERALL STUDY DESIGN

4.1 Overview of Study Design

The 12-months SCHEDULE main study was a prospective, multi-center, randomized, controlled, parallel group, open label study in de novo heart transplant recipients. The study consisted of two study periods, period 1 (HTx to week 7-11) and period 2 (week 7-11 to Month 12). Patients fulfilling the inclusion and exclusion criteria were randomized to one of two treatment groups: (i) conventional treatment with CsA, mycophenolate mofetil (MMF), and corticosteroids (Group A), or (ii) low-dose CsA, everolimus, MMF, and corticosteroids (Group B). After period 1, CsA was discontinued in Group B (experimental set-up with off-label use of everolimus), while the standard triple-drug immunosuppressive regimen was maintained in Group A.

In the 12-month SCHEDULE-study, 115 patients were randomized and treated. The patients were recruited from six transplant centres in Norway, Sweden and Denmark. The main study was followed by a 3-year follow-up visit in which 102 of the 115 patients participated. This 5 to 7-year follow-up visit is a further longtime follow-up examination of the patients participating in the SCHEDULE main study and the 3-year follow-up visit.

After completion of the 12-month SCHEDULE study, some patients have continued on the same immunosuppression and some of the patients have switched to alternative immunosuppressive treatment.

Patients who have participated in the 12-month SCHEDULE study and the 3-year follow-up visit and who are coming for an annual 5 to 7-year follow-up visit after randomization will be asked to participate.

The patients will be allocated to the same randomization group as in the 12-month SCHEDULE study for which stratified randomization and the following four strata were applied:

- mGFR ≤60 mL/min before transplantation AND mechanical assist device, Left Ventricular Assist Device (LVAD), Biventricular Assist Device (BiVad) or Extra Corporal Membrane Oxygenation (ECMO)
- mGFR ≤60 mL /min before transplantation AND no mechanical assist device
- mGFR >60 mL /min before transplantation AND mechanical assist device
- mGFR >60 mL /min before transplantation AND no mechanical assist device

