6.3 Hypotheses and Statistical Methods

6.3.1 Definitions

Baseline: Visit 6 (week 7-11)

Relative day: The relative day of an event is derived as follows:

Relative day = (Start date)-(Date of first administration of Investigational Medicinal Product (IMP))+1.

For days before the start date, calculate as Relative day = (Start date)-(Date of first administration of IMP).

Age: Date of Informed Consent at SCHEDULE main study-Birthdate

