6.5 Adjustment for Covariates

Baseline measurement for mGFR will be used as covariate and stratum as classification variable in the ANCOVA.

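### The primary ANCOVA adjusts for mGFR at Visit 6 (week 7-11), after the randomised regimens had diverged, so its estimate leaves out any Period 1 treatment effect carried by that value

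*Protocol*

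**What the plan says.** Protocol 4.4 specifies an ANCOVA with treatment and the randomisation strata as classification variables, and adds: "In addition, the mGFR values at baseline (Visit 6) will be used as covariate". SAP 6.3.5 repeats the model, SAP 6.3.1 supplies the definition "Baseline: Visit 6 (week 7-11", and SAP 6.5 confirms: "Baseline measurement for mGFR will be used as covariate and stratum as classification variable in the ANCOVA".

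On timing, Protocol 3 says: "The study consisted of two study periods, period 1 (HTx to week 7-11) and period 2 (week 7-11 to Month 12". On treatment, Protocol 4.2 says: "Patients in Group B commenced on an immunosuppressive regimen consisting of low dose everolimus and CsA, MMF and corticosteroids in period 1". Group A had CsA, MMF and corticosteroids in both periods.

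On the question asked, Protocol 1.2 wants to know "whether early initiation of everolimus and early elimination of CsA compared to standard immunosuppressive regimen including CsA can improve long-term renal function". SAP 3.1 times the outcome: "The primary endpoint is renal function as assessed by measured glomerular filtration rate (mGFR) 5-7 years after randomization". The null hypothesis in both documents is a plain equality of mean mGFR between arms at the 5-7-year visit.

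The only renal information from before randomisation in the model is the stratum, for example "mGFR ≤60 mL/min before transplantation AND mechanical assist device" (SAP 4.1). The PPS and extended PPS analyses repeat the same model (SAP 6.3.5).

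**The concern.** A covariate measured before randomisation cannot have been changed by treatment, so adjusting for it adds precision and leaves the target of estimation alone. Visit 6 mGFR does not have that protection. It is the endpoint variable itself, measured after some 7 to 11 weeks in which only Group B took everolimus and, according to Protocol 3, its CsA was low-dose. Protocol 1.1 names CNI nephrotoxicity as the motive for the strategy, so an early effect on mGFR is plausible.

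If there was one, the Visit 6-adjusted coefficient compares the arms as though they had reached week 7-11 with equal renal function. That suits the question of what CsA elimination does from week 7-11 onwards. It is narrower than the stated question, which includes early initiation and starts at randomisation. The estimate, confidence interval and p-value would then be too low for the whole strategy if Group B gained in Period 1, and too high if it lost. Neither document's visible text says that the primary result is conditional in this way.

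**Working it through.** **Inputs from the documents.** Covariate: Visit 6 mGFR (Protocol 4.4). Visit 6: week 7-11 (SAP 6.3.1). Period 1: transplantation to week 7-11 (Protocol 3). 115 patients were randomised and 102 were seen at 3 years (Protocol 3). SAP 4.2 gives no sample size, SD or effect, so there is no planned figure to reproduce.

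**Inputs assumed.** 45 per arm; within-arm SD 20 mL/min/1.73 m² at Visit 6 and at 5-7 years; slope b of 5-7-year on Visit 6 mGFR 0.4 to 0.8 (central value 0.6); treatment-caused Visit 6 difference d from -5 to +5; effect arising after Visit 6 of 8.

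**Step 1: the identity.** For a linear ANCOVA, expected coefficient = total effect - b × d. Only the treatment-caused part of the Visit 6 difference counts as d. A chance difference is not a bias, and adjustment rightly corrects it.

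**Step 2: size.** The smallest non-zero case is 0.4 × 1 = 0.4 and the largest is 0.8 × 5 = 4.0 mL/min, with the sign of d. At d = 0 the omitted part is zero.

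**Step 3: simulation at b = 0.6** (6,000 replicates per row; total = 8 + 0.6 × d):

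| d | Total effect | Planned model, mean estimate | Coverage of the total by the planned 95% CI |
|---|---|---|---|
| -5 | 5.0 | 7.97 | 86.7% |
| -3 | 6.2 | 8.08 | 91.7% |
| -1 | 7.4 | 8.01 | 94.7% |
| 0 | 8.0 | 7.97 | 95.0% |
| +1 | 8.6 | 7.90 | 94.3% |
| +3 | 9.8 | 8.00 | 91.8% |
| +5 | 11.0 | 8.09 | 86.9% |

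The planned model returns about 8 whatever d is. Over slopes 0.4 to 0.8, coverage is 94-95% at ±1, 84-94% at ±3 and 67-92% at ±5. Models without Visit 6 keep 94-96% throughout. With no effect in either period, the planned model rejects in 5.0% of runs and the strata-only model in 5.1%.

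Other assumed inputs give the same picture (102 patients, b = 0.5, d = +5, total 8 + 0.5 × 5 = 10.5): 7.97 with Visit 6 and 10.43 with strata only. If an unmeasured factor also drives both Visit 6 and later mGFR, the fitted slope is steeper than 0.5. In one such case the planned model averaged 6.7, against 10.5 with strata only.

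**Step 4: can the planned summaries settle it?** The chance SE of the Visit 6 difference is 20 × √(2/45) = 4.22, a 95% range of ±8.3. That is wider than any d considered here. Among replicates with an observed gap of +4 to +6, the planned model averaged 7.95 both when the gap was chance (truth 8.0) and when d = +5 (truth 11.0). The arm means at Visit 6 cannot tell the two cases apart.

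**Step 5: cost of leaving Visit 6 out.** At b = 0.6 the SE is 4.11 with strata only, against 3.46 with Visit 6. With no Period 1 effect, power for a true effect of 8 is 49% against 63%. In patient numbers the loss is 1 - (3.46/4.11)² = 29%. The planned model has equal or smaller total error until |d| reaches √(4.11² - 3.46²)/0.6, about 3.7; for slopes 0.4 to 0.8 the crossover stays at 3.6 to 3.7. At a chance gap of +4 to +6 the strata-only model averages 10.2 against a truth of 8.0.

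**The case against.** The case for the plan is substantial.

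- **No error is shown in this trial.** Every number for b, d and SD is assumed, and coverage at the central slope is still about 92% at ±3. This stands.
- **Visit 6 has a design rationale.** It marks the point at which CsA was withdrawn in Group B, and Protocol 1.1 describes the renal benefit in terms of everolimus with early CNI withdrawal. This stands for the elimination step. It does not cover early initiation, which the purpose also names.
- **The conditioning is disclosed, since the covariate is named.** True of the model. Neither document's visible text says how it changes the meaning of the result.
- **The planned summaries nearly supply the alternative.** Observed 5-7-year mGFR by arm, with n, mean and SD (SAP 6.3.2 and 6.3.5), lets a reader compute an unadjusted difference with SE 4.22, close to the 4.11 of a strata-only model. This largely stands. What is missing is a prespecified, strata-adjusted estimate with its interval and p-value.
- **A sensitivity analysis may sit in redacted text.** Parts of SAP 6.4 and 6.6 are blacked out, so this cannot be excluded.

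A reader might go further and infer that the primary model is invalid and must be replaced. The documents do not support that. The Period 1 effect is unknown, and the planned model has the smaller total error unless that effect exceeds about 3.6 to 3.7 mL/min. Power would fall from 63% to 49% in a cohort that cannot be enlarged. No visible text lists a continuous pre-transplantation mGFR among the data to be analysed. The study is also open and its 12-month and 3-year renal results are known, so changing the primary covariate now would itself invite criticism.

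**Conclusion.** The point holds as a gap between the stated question and what the primary model estimates. The covariate is measured after randomisation and after different treatment, so the primary estimate omits b × d. Under the assumed slopes and Period 1 effects that is 0.4 to 4.0 mL/min in either direction; it is zero if Period 1 did not change mGFR. A Period 1 effect that reaches later mGFR by a route other than Visit 6 mGFR stays in the estimate.

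Three other inferences would go too far. The documents do not show that the result is biased for or against everolimus, because they give no Visit 6 difference. They do not show a raised false-positive rate when treatment has no effect in either period; in simulation it is 5%. Nor is there an inconsistency over baseline: both documents use Visit 6 in the ANCOVA, and SAP 6.3.11 also reports laboratory differences from baseline.

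What is warranted is a supplementary analysis and a clear label.

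**What to change.** Keep the planned primary model. Before database lock, in Protocol 4.4 and SAP 6.3.5 and 6.5, with an entry in SAP 6.1:

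1. Add one named sensitivity ANCOVA of 5-7-year mGFR in the ITT set, with treatment and randomisation strata and without Visit 6 mGFR. Report the estimate, 95% CI and p-value, and repeat it in the PPS and extended PPS.
2. State that the Visit 6-adjusted estimate is conditional on week 7-11 mGFR, and that the model without Visit 6 estimates the effect of the whole strategy from randomisation.

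This should be settled before lock, because a choice between the two models made after seeing results would not be credible.

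**Cost.** One extra model and a few sentences. It needs no new data, since the strata are already in the primary model, and it takes no precision from the primary test. The added estimate is itself less precise (assumed SE about 4.1 against 3.5 at slope 0.6) and does not correct a chance imbalance at Visit 6, so the two results should be read together. Neither model deals with selection into analysis sets that require a 5-7-year assessment (SAP 5). If a redacted section already holds such a model, only the labelling remains to be done.
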